#### *7.6.1.3 New onset uncomplicated Grade 1 or Grade 2 diarrhea for Cycle 2 and beyond*

##### **Dietetic measures:**

- Stop all lactose-containing products.
- Drink 8 to 10 large glasses of clear liquids per day.
- Eat frequent small meals.
- Recommend low fat regimen enriched with bananas, rice, applesauce and toast until resolution of diarrhea.

##### **Pharmacological Treatment:**

- Administer loperamide: initial dose of 4 mg (2 tablets/capsules) with the first bout of diarrhea followed by 2 mg (1 tablet/capsule) every 4 hours or after every unformed stool (maximum 16 mg a day) and continue loperamide at this frequency until diarrhea free for 12 hours.
- For patients with persistent Grade 1 diarrhea on loperamide, Lomotil (diphenoxylate hydrochloride and atropine sulfate) 1 tablet (2.5 mg) every 6 to 8 hours may be added (or equivalent as approved by the Sponsor).
- For Grade 2 diarrhea (4 to 6 stools per day above baseline, despite intensive antidiarrheal therapy), consider adding octreotide (short-acting) 150 µg SC three times daily (TID); or after initial dose of short-acting octreotide, if well tolerated, a single dose of octreotide LAR 20 mg intramuscular (IM) (equivalent medication may be used with approval of the Investigator).

#### *7.6.1.4 For Grade 3 diarrhea with complicating features (dehydration and or hospitalization)*

##### **Dietetic measures:**

Same as above

##### **Pharmacological treatment:**

- Administer loperamide: initial dose of 4 mg (2 tablets/capsules) with the first bout of diarrhea followed by 2 mg (1 tablet/capsule) every 4 hours or after every unformed stool (maximum 16 mg a day) and continue loperamide at this frequency until diarrhea free for 12 hours. Then titrate the amount of loperamide used to keep diarrhea controlled (<4 stools/day). For patients with persistent Grade 1 diarrhea (<4 stools per day above baseline) on loperamide, Lomotil® (diphenoxylate hydrochloride and atropine sulfate) 1 tablet (2.5 mg) every 6 to 8 hours may be added (or equivalent as approved by PI).
- Administer octreotide (150 µg SC tid if dehydration is severe or at the treating physician's discretion, with dose escalation up to 500 µg SC TID).
- Use IV fluids as appropriate.
- Consider prophylactic antibiotics as needed (e.g., fluoroquinolones) especially if diarrhea is persistent beyond 24 hours or there is fever or Grade 3-4 neutropenia.
- Stool cultures should be done to exclude infectious causes of Grade 3 or 4 diarrhea or diarrhea of any grade with complicating features (dehydration, fever, and/or Grade 3 or 4 neutropenia) per the Investigator's discretion. Results from occult blood, fecal leukocyte stain, Clostridium difficile, Campylobacter, Salmonella, and Shigella testing, when performed, should be reported using the appropriate CRF.

#### **7.6.2 Permitted Concomitant Treatment**

- Any palliative and/or supportive care for cancer-related symptoms, which are not otherwise specified in the list of prohibited medication, is permitted at the Investigator's discretion.

- Standard therapies for preexisting medical conditions, medical and/or surgical complications and palliation. All medication(s) as well as previous hormonal therapy, dose and length of therapy should be recorded in the CRF.

### 7.6.3 Concomitant Treatment Prohibited in Combination with Neratinib

The following treatments are prohibited throughout the duration of the active (treatment) phase of the study:

- Any concurrent chemotherapy, radiotherapy (including palliative radiotherapy), surgery related to cancer, anticancer immunotherapy, or other anticancer treatments including other investigational agents, megestrol and hormonal agents.
- Concurrent use of strong CYP3A4 inducers/inhibitors (**Appendix F**) should be cautiously monitored.

### 7.6.4 Other concomitant medications with potential for interaction

Concomitant administration of neratinib and P glycoprotein (P-gp) substrates with a narrow therapeutic window should be monitored closely with the exception of loperamide. Co-administration of neratinib with digoxin could result in increased digoxin levels and associated digoxin toxicity. Co-administration of digoxin while patient is on neratinib is prohibited. Refer to **Appendix D** for a list of substrates and inhibitors of P-gp.

Patients using drugs known to cause QT/QTc prolongation should be monitored closely with serial electrocardiograms (ECG) at the Investigator's discretion. Refer to **Appendix E** for a summary of drugs known to have a risk of causing QT/QTc prolongation, potentially causing Torsade de Pointes (TdP).

Patients should avoid agents known to be strong cytochrome P450 (CYP) 3A4 inducers or inhibitors (e.g., ketoconazole) for the duration of the active stage/phase of the study. Patients should also avoid grapefruit/grapefruit juice and herbal remedies, including St John's Wort. Refer to Appendix F for a list of inhibitors and inducers of CYP isoenzymes.

Chronic immunosuppressive therapies should be avoided, including systemic corticosteroids. If unavoidable, patients taking such agents should be monitored closely. Steroids given for physiological replacement, as anti-emetics, or inhaled, as well as short course of oral/topical steroids given for allergic reactions or asthma flares, are allowed.

Patients taking oral coumarin-derivative anticoagulants (i.e., warfarin) should be monitored closely and their anticoagulant dose adjusted as needed.

The solubility of neratinib is pH dependent and treatments that alter gastrointestinal pH such as proton pump inhibitors (PPIs), H2-receptor antagonists, and antacids may lower the solubility of neratinib. It has been observed that a single 240-mg dose of neratinib combined with lansoprazole may decrease neratinib AUC by up to 70%. It is unknown whether separating PPI and a neratinib dose reduces the interaction. If an H2-receptor antagonist such as ranitidine is required, neratinib should be taken 10 hours after the H2-receptor antagonist dosing and at least 2 hours before the next dose of the H2-receptor antagonist. If antacids are necessary, the antacid dose and the neratinib dose should be separated by 2 to 4 hours.

#### 7.6.4.1 Additional Studies

##### **Geriatric assessment(GA):**

The comprehensive geriatric assessment questionnaires are listed in **Appendix H (Self Geriatric Assessment Measure – Patient Questionnaire)** and **Appendix I (Healthcare Professional Questionnaire)**. As part of the study initiation, the study team (including PI, nurses, and CRAs) will be trained on the use of geriatric assessment questionnaires as well as potential interventions based on the results. The GA results will be made available to treating physicians and nurse. The individual treating physician will follow up on the GA results using their best clinical judgment. Furthermore, if a patient scores 11 or greater (a potential indicator of cognitive impairment) on the Blessed Orientation Memory and Concentration Test, the results will be reported to the treating physician so that further work-up and treatment can be performed as they deemed medically appropriate. Furthermore, if the patient endorses depression or anxiety (score greater than or equal to 5), the doctor will be notified.

If patient's native language was not covered by the current language forms, Geriatric assessment form can be omitted with clear documentation.

##### **PK and peripheral blood biomarkers:**

Please refer to **Section 11** for PK and peripheral blood biomarkers correlative studies to be conducted under this protocol.

#### 7.7 Laboratory Studies/Monitoring Studies

##### **7.7.1 Required Clinical, Laboratory and Disease Evaluation at Baseline**

Complete blood count and differential, comprehensive metabolic panel (including sodium, potassium, chloride, bicarbonate, blood urea nitrogen, creatinine, glucose, calcium, ALT, AST, alkaline phosphatase, total bilirubin, total protein, and albumin), must be performed within 14 days of enrolling on trial.

A full history and physical exam including demographics, medical history, concurrent medications, vital signs, height measurement, weight measurement, and performance status analysis must be done within one week of enrolling on trial.

Radiologic evaluation including computed tomography (CT) of the chest, abdomen, and pelvis; or combined PET-CT with a diagnostic CT component, must have been performed within 30 days of study enrollment. If measurable disease is present, tumor measurements must be performed and reported from this scan. Central review is not required for treatment decisions in individual subjects.

The patient must complete a Geriatric Assessment prior to starting therapy (see Appendix I). If patient's native language was not covered by the current language forms, Geriatric assessment form can be omitted with clear documentation.

Cardiac imaging (either by echocardiogram or MUGA scan) with a reported left ventricular ejection fraction must be obtained within 30 days of study enrollment. Regardless of where the baseline evaluation is performed, future cardiac evaluation must be performed using only the

same modality as the baseline evaluation. A baseline EKG before starting treatment is also required.

### **7.7.2 Studies Obtained During the Trial**

#### ***7.7.2.1 Disease evaluation***

CT scans of the chest, abdomen, and pelvis; or PET-CT with a diagnostic CT component must be performed every 12 weeks ( $\pm 1$  week) in the absence of symptoms to document disease response or progression. In the presence of symptoms, these tests may be performed at the discretion of the treating physician.

#### ***7.7.2.2 Cardiac evaluation***

Echocardiogram or MUGA scan must also be performed every 12 weeks ( $\pm 1$  week) in the absence of symptoms. The modality must be the same as the modality used in the baseline cardiac evaluation. In the presence of symptoms, or in the setting in which a prior study shows an abnormality requiring confirmation, echocardiogram or MUGA will be done at the discretion of the treating physician.

Complete blood count with differential and complete metabolic panel must be performed every four weeks ( $+/- 1$  wk). If screening laboratories are performed within 14 days of the first study treatment, repeat laboratory tests will not be required before Week 1, Day 1.

#### ***7.7.2.3 Pharmacokinetics***

Please refer to section 11.1 for details of sample collection, labeling, storage. Shipping, and analysis of PK samples.

#### ***7.7.2.4 Peripheral Blood Biomarkers Predicting Chemotherapy Tolerability***

Please refer to section 11.2 for details of sample collection, labeling, storage and analysis of peripheral blood biomarker samples .

### **7.7.3 Monitoring Studies**

#### ***7.7.3.1 Toxicity Evaluation***

Because early toxicity is common during cycles 1 and 2 with neratinib, patients will have a focused visit with a study nurse to evaluate for new toxicities (Week 2, Week 3). A complete case report form is not required for these short visits, which are designed to ensure that interventions may occur should toxicity be apparent.

#### ***7.7.3.2 Adherence Evaluation***

Adherence to neratinib will be measured by pill count every 4 weeks during the first five cycles during the investigator assessment, and every twelve weeks thereafter, as well as by patient self-report in dedicated patient diaries evaluated at the same time as pill count. In the event of discrepancy in these two measures of adherence, we will follow whichever indicates the lower measure of adherence (i.e. if patient states they took 26 of 28 doses, but only 20 doses are

missing, we will count the patient as having taken only 20 days. Alternatively, if 26 doses are missing, but the patient stated she only took 20 doses, we will count the patient as having taken only 20 doses.) All toxicity related dose interruptions or reductions, hospitalizations, and adverse events will be noted. Subjects will be followed for toxicity outcomes for an additional 30 days after stopping the drug, and until resolution of all grade  $>3$  toxicities.

#### 7.7.3.3 *Geriatric Assessment*

Geriatric assessment surveys will be administered at baseline( $+$ / $-$  7 days), after every four cycles, cycle 4 day 1( $+$ / $-$  7 days), cycle 7 day 1( $+$ / $-$  7 days) and at the end of the study ( $+$ / $-$  7 days) if not performed in the previous month (see Appendix I for Geriatric Assessment Survey). If patient's native language was not covered by the current language forms, Geriatric assessment form can be omitted with clear documentation.

#### 7.7.3.4 *Survival Status*

Patients will be followed indefinitely to establish overall survival. All participants enrolled on the study will be informed that their medical condition will be followed indefinitely. In order to obtain survival status on the enrolled patients we will need the patient's first and last name, middle initial, social security number, date of birth, and gender. This information will be securely transferred to the primary coordinating institution (City of Hope) and will be kept in a separate password protected file, which will only be linked for the purpose of establishing survivor status. The investigators will utilize the Social Security Death Index and the National Death Index to establish survival status. Survival analysis will be conducted once a year.

## **8.0 Dose Delays/Modifications for Adverse Events**

---

Patients will be treated per protocol or until disease progression or withdrawal from treatment due to unacceptable adverse events or treatment consent withdrawal. At each study assessment, subjects are to be evaluated for evidence of drug-related adverse events.

In all cases where the subject is withdrawn due to unusual or unusually severe adverse event considered related to neratinib, the Investigator must report the withdrawal as a Serious Adverse Event.

Treatment may be delayed for up to 4 weeks, to allow for resolution of toxicity except in the event of those toxicities described below in which cases treatment must be discontinued permanently (see **Table 7**).

Recommended dose reductions for the -1 and -2 dose levels of Neratinib are listed as following:

Dose level	Neratinib
Starting dose	240mg
-1	160mg
-2	120mg

If a dose of neratinib is held, study procedures for that cycle will proceed on schedule as planned, without any delay. This also applies to tumor assessments, which should continue to be done every 12 weeks, starting from the first dose of neratinib until the first planned tumor assessment at 12 weeks ( $\pm 1$  wk), and then after every subsequent 12 weeks ( $\pm 1$  week) of treatment regardless of any changes in dose or occurrence of AEs. Missed dose(s) of neratinib (i.e., any

dose that is not administered within the protocol-defined administration window) will not be made up. The dose adjustment guidelines represent the minimum set of measures that investigators must follow. However, additional measures may be taken as necessary, for certain patients per the Investigator's medical judgment. All dose modifications/adjustments should be documented in the patient's source file.

Once neratinib dose has been reduced for a patient, all subsequent cycles must be administered at that dose, unless further dose reduction is required. Dose re-escalation is not permitted.

If a patient developed AE requiring dose reduction while on neratinib dose level of 120mg, neratinib will be discontinued.

## 8.1 General Toxicities

Detailed guidelines for dose adjustments of neratinib for general toxicities (exclude alopecia) are shown in **Table 7**. Grade 2 or 3 toxicities that are unrelated to neratinib will be excluded from the dose adjustment.

## 8.2 Gastrointestinal Toxicity

Neratinib dose adjustment guideline is listed in **Table 8**.

## 8.3 Pulmonary Toxicity

Guidelines for adjusting doses of neratinib in the event of pulmonary toxicity are shown in **Table 9**.

Interstitial lung disease, which can sometimes be fatal, has been reported with other oral tyrosine kinase inhibitors that target HER1 ± HER2, including lapatinib, gefitinib and erlotinib. Rare cases of pneumonitis (0.6%) and lung infiltration (0.4%) have been reported in patients treated with neratinib monotherapy, and were considered drug-related. Patients receiving neratinib should be monitored for acute onset or worsening of pulmonary symptoms such as dyspnea, cough and fever and treated appropriately.

**Table 7: General Toxicities Requiring Dose Adjustment of Neratinib\***

NCI CTCAE v.4.0	Action
Grade 3 adverse reaction	
1st appearance	Hold neratinib until event resolves to Grade $\leq 1$ ; then resume neratinib at one dose level lower, lowest dose of neratinib is 120mg.
2nd appearance	Hold neratinib until event resolves to Grade $\leq 1$ ; then resume neratinib at one dose level lower, lowest dose of neratinib is 120 mg
3rd appearance	Discontinue neratinib permanently.
Grade 4 adverse reaction	

Any	Discontinue neratinib permanently.
-----	---

Based on NCI CTCAE v.4.0: National Cancer Institute Common Terminology Criteria for Adverse Events Version 4.0.

\* Grade 2 or 3 toxicities that are unrelated to neratinib will be excluded from the dose adjustment.

**Table 8: Gastrointestinal Toxicities Requiring Dose Adjustment of Neratinib**

NCI CTCAE v.4.0	Actions
Grade 1 Diarrhea: Increase of $\leq 3$ stools per day over baseline. OR Grade 2 Diarrhea: Increase of 4-6 stools per day over baseline. Lasting <math>\leq 5</math> days	Adjust antidiarrheal treatment per the guidelines for management of diarrhea at the first onset of diarrhea (refer to Section 7.6.1.1 ). Instruct patient to follow dietetic recommendations in the guidelines for management of diarrhea. Fluid intake of $\sim 2$ L/day should be maintained to avoid dehydration.
Grade 3 Diarrhea: Increase of $\geq 7$ stools per day over baseline; incontinence; hospitalization indicated; limiting self-care and activities of daily living. Lasting <math>\leq 2</math> days	Adjust antidiarrheal treatment per the guidelines for management of diarrhea at the first onset of diarrhea (refer to Section 7.6.1.1 ). Hold neratinib until recovery to Grade $\leq 1$ or baseline. Instruct patient to follow dietetic recommendations of the guidelines for management of diarrhea. Fluid intake of $\sim 2$ L/day should be maintained by IV, if needed. If recovery occurs: 
 
<math>\leq 1</math> week after withholding treatment, resume neratinib at the next reduced dose level
 
Within 2-4 weeks after withholding treatment, reduce neratinib dose at the next lower dose.
 
 If event occurs a second time and the neratinib dose has not already been decreased, reduce neratinib dose to next lower dose level. If subsequent events occur, reduce the dose of neratinib to the next lower dose level. Once the event resolved to Grade $\leq 1$ or baseline, start loperamide 4 mg with each subsequent neratinib administration.

Grade 3 Diarrhea: lasting >2 days despite treatment with optimal medical therapy, or associated with fever, dehydration OR Any Grade 4 Diarrhea: Life-threatening consequences: urgent intervention indicated. (would recommend d/c)	Recommend permanently discontinue neratinib OR if Investigator deems it to be in the patient's best interest to continue, hold neratinib until AE resolved to Grade $\leq 1$ ; then resume neratinib at 120 mg.
--	--

Based on NCI CTCAE v.4.0: National Cancer Institute Common Terminology Criteria for Adverse Events Version 4.0.

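### The two grade 3 diarrhea rows of Table 8 do not place every episode under exactly one neratinib rule: some short episodes can meet both rows, and some longer ones meet neither

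*Combined protocol and SAP*

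**What the plan says.** Section 8.2 sends gastrointestinal toxicity to Table 8, which has two rows for grade 3 diarrhea.

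- **Short row.** It describes grade 3 by stool count and by "incontinence; hospitalization indicated; limiting self-care and activities of daily living", and is limited to episodes of at most 2 days. Neratinib is held until grade 1 or baseline, and fluid intake "should be maintained by IV, if needed". On recovery the instruction is to "resume neratinib at the next reduced dose level". Fever and dehydration are not excluded.
- **Long-or-complicated row.** It takes grade 3 diarrhea of more than 2 days "despite treatment with optimal medical therapy, or associated with fever, dehydration", together with any grade 4 diarrhea. The action is "Recommend permanently discontinue neratinib" or, "if Investigator deems it to be in the patient's best interest to continue, hold" until grade 1 or less and restart at 120 mg. Table 8 does not define optimal medical therapy.

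Three other places bear on the same episode:

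- Table 7 (Section 8.1, general toxicities) has a grade 3 rule with no condition on duration, therapy or complications: hold and go one level lower at the first and second appearance, discontinue at the third.
- Section 7.6.1.2 refers grade 3 diarrhea in Cycle 1 to Tables 7 and 8 together, with no order between them.
- Section 8.0 sets the levels at 240, 160 and 120 mg, requires discontinuation if a reduction is needed at 120 mg, forbids re-escalation, and makes the guidelines an obligatory minimum.

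Section 7.6.1.4 covers supportive care for complicated grade 3 diarrhea and gives no neratinib action.

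**The concern.** The rows of a dose-modification table should divide the possible episodes so that each has one rule. Here one row is defined by duration alone. The other is defined by duration combined with prior therapy, or by a complication. Criteria built on different axes can overlap and can leave holes.

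Two investigators following the protocol could then handle the same episode differently. Because re-escalation is forbidden, a reduction or discontinuation cannot be reversed later. Diarrhea is the toxicity the trial is most concerned with, and every patient starts at 240 mg. The choice of row feeds the rates of reduction and discontinuation named in Section 2.2, and the reduction rate estimated in Section 15.3 and at the 20-patient interim review (Section 15.2.1).

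**Working it through.** The plan gives no figure to reproduce, so the check is one of logic. Each grade 3 episode is classified on three yes/no features taken from Table 8: longer than 2 days, on optimal medical therapy, and accompanied by fever or dehydration. That gives 2 × 2 × 2 = 8 combinations.

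The short row (S) applies when the episode is not longer than 2 days. The long-or-complicated row (L) can be read in two ways:

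- Reading 1, the natural one: fever or dehydration stands alone. L = (longer than 2 days and optimal therapy) or complication.
- Reading 2: the duration governs both conditions. L = longer than 2 days and (optimal therapy or complication).

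| >2 days | Optimal therapy | Fever/dehydration | Reading 1 | Reading 2 |
|---|---|---|---|---|
| no | no | no | S | S |
| no | yes | no | S | S |
| no | no | yes | S and L | S |
| no | yes | yes | S and L | S |
| yes | no | no | none | none |
| yes | no | yes | L | L |
| yes | yes | no | L | L |
| yes | yes | yes | L | L |

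Reading 1 gives 5 combinations in one row, 2 in both and 1 in neither. Reading 2 gives 7 in one row, 0 in both and the same 1 in neither. The overlap therefore depends on the reading; the gap does not. These are counts of combinations, not of patients.

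For an episode in both rows, the action after the hold, by current dose (Table 8 with Section 8.0), is:

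| Current dose | Short row | Long-or-complicated row | In common |
|---|---|---|---|
| 240 mg | 160 mg | discontinue (recommended) or 120 mg | nothing |
| 160 mg | 120 mg | discontinue (recommended) or 120 mg | 120 mg |
| 120 mg | discontinue | discontinue (recommended) or 120 mg | discontinue |

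For an episode in neither row, Table 7 would supply a rule if it applies to diarrhea. Sections 8.1 and 8.2 separate general from gastrointestinal toxicity, which suggests that it does not. Section 7.6.1.2 cites it for Cycle 1, which suggests that it does.

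On size, one patient is 1/40 = 2.5 percentage points of a final rate and 1/20 = 5 points at the interim review.

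**The case against.** The best defense is that the table works in practice. Both rows can begin with a hold. The second row only recommends discontinuation and leaves an alternative to the investigator, so removing the overlap would not make outcomes uniform. Reading 2 removes the overlap altogether. Section 8.0 allows measures beyond the minimum, so an investigator facing both rows may take the more cautious one. Antidiarrheal prophylaxis is mandatory in Cycle 1 and treatment is to be adjusted at onset, so more than 2 days without optimal therapy should be uncommon.

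Much of this stands, and it limits what can be claimed. A reader might infer any of the following, and the documents do not support them:

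- *The rows give opposite actions.* They give different ones, fully so only at 240 mg.
- *A patient in the gap has no rule at all.* Table 7 may apply.
- *Hospitalized patients are assigned to the milder row.* The mention of hospitalization there belongs to the description of grade 3 itself and does not assign patients to a row. The mention of IV fluids likewise maintains intake and does not show that dehydrated patients belong in that row.
- *Loperamide held for constipation is the typical gap case.* Section 7.6.1.1 generally resumes it after the first bowel movement, and a patient with more than 2 days of grade 3 diarrhea is past that point.

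What does not stand is that the text settles the matter. Nothing says which reading of the second row is meant. Permission to do more than the minimum is not an order of precedence. Without a definition of optimal medical therapy, a site cannot tell where the gap begins.

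**Conclusion.** The point holds as a drafting inconsistency in a safety rule. The gap exists on either reading of Table 8. The overlap exists on the natural reading, and there the actions differ at every dose level, with nothing in common after the hold at 240 mg.

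Its size in patients cannot be derived. With the 12–16% rate of grade 3 diarrhea under prophylaxis quoted in Section 10.2.1, assumed to carry over to this older population, 40 × 0.12 = 4.8 to 40 × 0.16 = 6.4 patients would have grade 3 diarrhea. At the 30% used to design Table 17, the figure is 40 × 0.30 = 12. The affected patients are some part of these, possibly none. A reader might try to go further with Table 4, dividing dehydration counts by grade 3/4 diarrhea counts (18/132 = 14%, 52/132 = 39%). The table does not cross-classify dehydration by diarrhea grade or duration, so those ratios do not measure the overlap.

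The primary endpoint and the Table 17 boundary are unaffected, because the episode counts the same whichever row is used. No sample-size or error-rate figure changes. What can shift is the split between reduction and discontinuation, and with it the safety of the individual patient.

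**What to change.** Amend the wording so that each grade 3 diarrhea episode falls under exactly one rule:

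1. In Table 8, state whether the condition of more than 2 days also governs fever and dehydration, so that it is clear which row takes a short episode with either.
2. State which row covers an episode of more than 2 days in a patient not on optimal medical therapy, and say what that term means.
3. State how Table 8 relates to Table 7 for grade 3 diarrhea, and bring the Cycle 1 cross-reference in Section 7.6.1.2 into line.

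Which action belongs to which episode is for the investigators to decide.

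Two additions are optional: a case report form field for the row applied, so that reductions and discontinuations can be traced to a rule, and one list of complicating features across Table 8 and Section 7.6.1.4.

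The cost is a wording amendment, plus one data field if the first option is taken. No patients, visits or procedures are added.
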